8.10 Medical-Surgical Procedures and Clinical Investigation Follow-up

The Investigator will include in the study those patients who, at the selection visit (Visit 0), meet all eligibility criteria. It is understood that, given the retrospective nature of the study and considering that the consent of eligible patients was obtained a priori, patients will not attend the selection visit nor any subsequent visits. Furthermore, during the selection visit (Visit 0), the Investigator will collect the patient's demographic data and medical history.

The data to be collected are as follows:

- Demographics and BMI
- Medical history
- Indication(s) treated
- Deformity parameters:
 - hip-knee-ankle angle (HKA)
 - anatomical lateral distal femoral angle (aLDFA)
 - mechanical axis deviation (MAD)
 - mechanical lateral distal femoral angle (mLDFA)
 - mechanical medial proximal tibial angle (mMPTA)
 - lateral distal tibial angle (LDTA)
 - fibular station
 - femur, tibia, fibula length
 - tibia-to-fibula ratio
 - femur-to-tibia ratio

Subsequently, data of interest related to the surgery for plate implantation (Visit 1) and to the treatment period — i.e., the two postoperative follow-up visits (Visits 2 and 3) up to plate removal (Visit 4) — will be collected. In particular, the following data will be gathered:

- Age at surgery
- Surgical details (duration, complications, postoperative X-ray) and data related to the implanted device(s) (i.e., quantity, type, and size)
- Concomitant medications and treatments
- Achievement of the treatment objective
- Treatment duration (calculated from implantation to removal)
- Complications (both device-related and non-device-related, leading or not to premature removal or unplanned surgery).

The course of treatment will be monitored as per routine clinical practice, and data corresponding to the follow-up visit, scheduled on average 4 months after plate removal (Visit 5), will be collected. At the follow-up visit, the following additional information will be recorded:

[figure not shown]
- Concomitant medications and treatments relevant to the study
- Status of the corrected deformity
- Deformity rebound
- Complications/Adverse events occurring after plate removal.

The Clinical Investigation data will be recorded in the patient's medical record and entered into a validated electronic data capture system provided by Orthofix Srl.

Note:

The visits and procedures described above are summarised in the patient treatment flowchart and in the table of procedures applicable to each visit.

8.11 Patient Treatment Flowchart

The patient treatment schedule follows the routine clinical practice of the participating Centre. However, certain visits may not be applicable depending on the type of patients included in the study.

8.12 Table of procedures

PHASE		ENROLLMENT	TREATMENT				FOLLOW UP
VISIT	Number	Visit 0	Visit 1	Visit 2	Visit 3	Visit 4	Visit 5
	Type	Selection	Implant	1° Follow up	2° Follow up	Removal	Follow up post removal
Selection Criteria Verification		x	x	x	x	x	x
Demographics		x					
Medical History		x					
X-rays		x				x	
Technical Characteristics of the Device			x				
Device Implantation			x				
Safety Measures			x	x	x	x	x
Benefit Measures		x				x	

8.13 Foreseeable Factors That Could Have Affected the Results

This Clinical Investigation is retrospective in nature; therefore, the clinical protocols observed are those applied at the participating Centre during the observation period of the Study.

The use of tension band plates for the treatment of angular deformities or limb length discrepancies is based on careful postoperative monitoring to avoid foreseeable complications, such as secondary deformity due to overcorrection, recurrence of deformity, or accidental physeal fusion. It is necessary to allow sufficient time for the plate to achieve its optimal effect on growth deceleration: studies suggest that its ability to slow growth is lower during the first 6–12 months, until adequate tension has accumulated across the plate to enable temporary compression of the growth plate.

In this Clinical Investigation, the enrolled patients correspond to the paediatric population without age restrictions, as indicated in the Instructions for Use. Based on these considerations, two factors are known that may compromise outcomes and the interpretation of the results, namely:

- The risk of inducing unintended physeal fusion, particularly if the plate remains implanted for more than two years. This can become a greater problem if a child is treated at a very early age, as premature unintended physeal fusion would have a significant impact on overall limb growth.
- The need for a second treatment if the procedure is performed at a very early age. This eventuality may particularly arise in cases of deformities due to metabolic or genetic disorders. Once the plate is removed, the angular deformity may recur (rebound effect).

8.14 Discontinuation and Withdrawal of Subjects from the Clinical Investigation

A patient will be considered prematurely discontinued from the study if, during the collection of data related to the visits following screening, the Investigator becomes aware that one of the inclusion or exclusion criteria is no longer fulfilled.

Patients prematurely discontinued will be recorded in the case report form through the dedicated discontinuation visit. The Investigator will be required to notify the Sponsor of all prematurely discontinued patients and, if the patient is not evaluable, i.e., discontinued before plate removal, may agree with the Sponsor on the replacement of the patient according to the procedure described below.

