8.6.1 Inclusion criteria

A patient will be considered eligible for participation if:

- he/she has been diagnosed with an angular deformity or a femoral and/or tibial length discrepancy;

- at the time of treatment, he/she was younger than 18 years of age;
- at the time of treatment, the growth plates of the treated limb(s) were not yet closed;
- in the opinion of the Investigator, the angular deformity and/or length discrepancy represented a valid indication for surgical treatment with tension band plates;
- the deformity was treated with the 8-Plate Plus, in accordance with the manufacturer's Instructions for Use;
- the treatment with the 8-Plate Plus was completed and the patient underwent at least one follow-up visit after plate removal;
- the clinical data of the patient required for the evaluation of the device's safety and clinical benefit are still available.

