8.15 Patients Replacement

Subject to prior notification to the Sponsor, and no later than the study database lock, non-evaluable patients may, at the Investigator's discretion, be replaced with a patient who will be assigned a new and unique identification code.

This procedure is intended solely to increase the likelihood of achieving the planned sample size in terms of evaluable implants. It is understood that the Sponsor will also collect, retain, and analyse the data of patients who were prematurely discontinued and subsequently replaced.

9 Clinical Investigation Monitoring Plan

In order to ensure the proper conduct of the study and the accurate recording of study data, at least the following monitoring visits will be foreseen:

- site initiation visit;
- one monitoring visit during the active conduct phase of the study;
- site close-out visit.

It is understood that, if necessary, the Sponsor reserves the right to perform additional monitoring visits during the active phase of the study.

Prior to each visit, the monitor will contact the Investigator to verify availability and schedule the visit date, and will subsequently send written confirmation specifying the purpose of the visit and any documents to be made available.

At each visit, the monitor shall:

- check the updating of study documentation;
- verify that data collection related to the Clinical Investigation is being conducted appropriately and that data are recorded and reported in compliance with this Clinical Investigation Plan, Good Clinical Practice (GCP), and applicable regulations;
- verify the accuracy of the data entered into the case report form against the source data;
- implement any necessary corrective actions.

Note: Written Monitoring Plan

For this type of Clinical Investigation, which is single-centre, observational, and retrospective, a separate written Monitoring Plan is not foreseen, since all necessary information is already included in the Clinical Investigation Plan.

Note:

The Sponsor intends to monitor all reported data related to the inclusion and exclusion criteria, the study endpoint variables, and all information regarding serious and non-serious adverse events. If deemed appropriate and necessary, other study data may also be subject to monitoring.

10 Documentation

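### Eligibility is re-judged while complications are being read, and dropped patients may be replaced with no order for the substitute and no stated place in the primary rate, so outcome-informed selection is not prevented

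*Combined protocol and SAP*

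**What the plan says.** Section 5 states that the clinical data are already in the hospital records. Section 8.6.1 admits a patient only if "the treatment with the 8-Plate Plus was completed and the patient underwent at least one follow-up visit after plate removal".

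In Table 8.12 the row "Selection Criteria Verification" is marked at every visit from 0 to 5, and the safety row is marked at Visits 1 to 5. Section 8.14 discontinues a patient if, while post-screening visits are being collected, "the Investigator becomes aware that one of the inclusion or exclusion criteria is no longer fulfilled". It adds that the Investigator, "if the patient is not evaluable, i.e., discontinued before plate removal, may agree with the Sponsor on the replacement of the patient".

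Section 8.15 then says "non-evaluable patients may, at the Investigator's discretion, be replaced with a patient who will be assigned a new and unique identification code", with the condition "Subject to prior notification to the Sponsor, and no later than the study database lock". Its stated purpose is to help reach the planned number of evaluable implants. It also says that the Sponsor will "collect, retain, and analyse the data of patients who were prematurely discontinued and subsequently replaced".

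Section 16 plans one percentage with a 95% confidence interval for the primary endpoint. It names no analysis set. Section 8.4 defines that endpoint per subject.

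**The concern.** The discontinuation and replacement rules read like those of a prospective trial, applied here to finished charts. A correctly enrolled patient has already had the plate removed and a later visit, so cannot clinically stop before removal. The remaining route into that category is a criterion judged unmet while the earlier visits are being abstracted. Some criteria are objective, such as age and open growth plates. Others need judgement: use according to the Instructions for Use, a contraindication, or whether the records allow evaluation. That judgement is made on the same pages that record complications.

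If a patient with a complication were discontinued, left out of the percentage and replaced by one without, the numerator would fall and the denominator would stay full. The rule acts on whole patients and so also reaches hardware failures. This makes it separate from the exclusions of serious events in section 8.5. No bad faith is needed: knowing the outcome can influence a judgement about eligibility.

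**Working it through.** **The text, step by step**

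1. *Can outcomes be seen when eligibility is re-judged?* Yes. The data exist already (section 5), and Table 8.12 places verification and safety measures in the same columns for Visits 1 to 5.
2. *Who can be replaced?* Only patients discontinued before plate removal (8.14). A failure found while abstracting Visit 5 does not qualify.
3. *Who decides?* Section 8.14 speaks of agreement with the Sponsor; section 8.15 of the Investigator's discretion after notification. The two can be read together but do not say the same thing.
4. *Which chart comes next?* Neither section says. Section 5.2 says only that the Investigator selects eligible patients.
5. *Are dropped patients counted?* Section 8.15 promises analysis of replaced patients without naming the analysis. Discontinued patients who are not replaced are not mentioned. Section 8.14 labels the replaceable patients not evaluable, and section 16 does not settle the matter.

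**Inputs for the arithmetic**

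- Expected rate 3%, upper limit to stay below 12%, exact binomial method, 70 implants in about 40 patients (8.7 and 16).
- One swap: an assumption.

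**The plan's own figure**

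For x events in n, the two-sided 95% Clopper-Pearson upper limit is the 0.975 quantile of Beta(x + 1, n − x). Three per cent of 70 is 2.1, rounded to x = 2. With n = 70 this gives 9.94%, the plan's figure exactly.

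**One swap at 40 patients** (the endpoint is per subject)

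| Handling of the event patient | x/n | Rate | Upper limit |
|---|---|---|---|
| No swap | 1/40 | 2.50% | 13.16% |
| Replaced, not counted | 0/40 | 0% | 8.81% |
| Replaced, still counted | 1/41 | 2.44% | 12.86% |

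The 0/40 limit can be checked by hand: 1 − 0.025^(1/40) = 8.81%.

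**One swap at 70 units** (the plan's sample-size basis)

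| Handling of the event case | x/n | Upper limit |
|---|---|---|
| No swap | 3/70 | 12.02% |
| Replaced, not counted | 2/70 | 9.94% |
| Replaced, still counted | 3/71 | 11.86% |

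Here the limit falls just under 12% even when the case is kept, because the denominator grows by one.

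**Worst-case bound at 40 patients**

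The upper limit is below 12% only with 0 events. At a true rate of 3% the chance of that is 0.97^40 = 29.6%. If one event patient could always be swapped out uncounted, 0 or 1 events would suffice: 0.97^40 + 40 × 0.03 × 0.97^39 = 29.6% + 36.6% = 66.2%. At a true rate of 12% the same calculation goes from 0.6% to 3.9%. These are ceilings for one swap, not forecasts.

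**The case against.** The strongest reply is that section 8.15 keeps replaced patients' data and promises to analyse them. A reader might infer from the replacement rule that a patient with a complication leaves the safety rate. The documents do not establish that. If the patient is counted, one event among 40 becomes 1/41, with an upper limit of 12.86%, which stays above 12%. This part of the reply stands: the fall to 8.81% is conditional. It does not close the gap, because the promise names no denominator and omits discontinued patients who are not replaced.

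A reader might also infer that the Investigator is given the choice of substitute. The discretion in section 8.15 concerns whether to replace. Free choice of the next chart follows only from the absence of a rule.

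Other safeguards are real. Discontinuations are recorded at a dedicated visit in the case report form and notified to the Sponsor (8.14). Codes are sequential (5.1, 8.8). Eligibility, endpoint and adverse-event data are to be monitored (section 9), and the database keeps an audit history (section 11). A swap would leave a trail. But these measures document a replacement and check its accuracy; they do not stop eligibility being judged with the outcome in view.

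Replacement is also confined to patients discontinued before plate removal, a group that may be nearly empty. The documents give no frequency, and nothing shows that a complication would prompt a discontinuation. Finally, 12% is a literature bound used to size the study, not a declared success criterion, so no formal decision would be reversed.

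**Conclusion.** The point holds in a limited form. The stated rules allow eligibility to be re-judged and substitutes to be entered while outcomes are visible, and they do not fix whether dropped patients stay in the primary percentage. Outcome-informed entry is not prevented; outcome-informed exit is left open.

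With one event in 40 patients and one assumed swap, the unstated analysis set alone decides between an upper limit of 8.81% and one of 12.86%. How many swaps would occur, if any, is unknown. The matter should be corrected, since a single patient can move the reported interval this far and the remedy is mostly wording. It is not evidence that the rate will be biased.

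**What to change.** 1. **8.12 and 8.14.** Complete and lock eligibility before complication and outcome data are abstracted. Use baseline and implantation information, plus only the existence and dates of plate removal and of a post-removal visit, and the availability of records. The later dates are needed because 8.6.1 requires completed treatment, so a check limited to information up to implantation would not work. After the lock, remove a patient only for an objective criterion shown to have been unmet at implantation (for example age, closed growth plates, or device not implanted), and list the reason and event status.
2. **8.15.** Delete replacement, or take only the next eligible patient in implantation-date order. Reconcile 8.14 and 8.15 on who decides.
3. **Section 16.** Define the primary safety set as every enrolled patient who received the 8-Plate Plus, including those discontinued or replaced, with events counted up to the last record. List patients who never received the device without counting them. Report the rate without discontinued patients as a sensitivity analysis.

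The cost is wording in four sections and the discipline of abstracting in two steps. No patient contact is needed. The downside is that a few imperfectly eligible patients stay in the main rate; the sensitivity analysis shows their effect.

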8.15 Patients Replacement

Subject to prior notification to the Sponsor, and no later than the study database lock, non-evaluable patients may, at the Investigator's discretion, be replaced with a patient who will be assigned a new and unique identification code.

This procedure is intended solely to increase the likelihood of achieving the planned sample size in terms of evaluable implants. It is understood that the Sponsor will also collect, retain, and analyse the data of patients who were prematurely discontinued and subsequently replaced.

9 Clinical Investigation Monitoring Plan

In order to ensure the proper conduct of the study and the accurate recording of study data, at least the following monitoring visits will be foreseen:

- site initiation visit;
- one monitoring visit during the active conduct phase of the study;
- site close-out visit.

It is understood that, if necessary, the Sponsor reserves the right to perform additional monitoring visits during the active phase of the study.

Prior to each visit, the monitor will contact the Investigator to verify availability and schedule the visit date, and will subsequently send written confirmation specifying the purpose of the visit and any documents to be made available.

At each visit, the monitor shall:

- check the updating of study documentation;
- verify that data collection related to the Clinical Investigation is being conducted appropriately and that data are recorded and reported in compliance with this Clinical Investigation Plan, Good Clinical Practice (GCP), and applicable regulations;
- verify the accuracy of the data entered into the case report form against the source data;
- implement any necessary corrective actions.

Note: Written Monitoring Plan

For this type of Clinical Investigation, which is single-centre, observational, and retrospective, a separate written Monitoring Plan is not foreseen, since all necessary information is already included in the Clinical Investigation Plan.

Note:

The Sponsor intends to monitor all reported data related to the inclusion and exclusion criteria, the study endpoint variables, and all information regarding serious and non-serious adverse events. If deemed appropriate and necessary, other study data may also be subject to monitoring.

10 Documentation

During the site initiation visit, the monitor will provide the Principal Investigator responsible for the Clinical Investigation with a file containing all the paper documentation required for study management, namely:

- Clinical Investigation Plan with related Synopsis and appendices;
- copy of the approval from the relevant Ethics Committee;
- one original copy of the signed and authorised financial agreement;
- contact details for the participating Site;
- information regarding the medical device under investigation (Instructions for Use and surgical technique);
- certification of the CE marking of the device;
- one copy of the case report form;
- access credentials for the eCRF and user manuals for the platform.

Note:

The monitor will also provide an electronic, non-modifiable copy of all study documentation for consultation and printing, as required by the Investigator.

As required by Good Clinical Practice guidelines:

- in order to prevent accidental or premature destruction of study documents, the Investigator shall store the file in a secure environment with controlled access;
- for the entire duration of the Clinical Investigation, study documentation must be kept up to date and made available during monitoring visits;
- study documentation must be retained for as long as possible and, at a minimum, for 7 years after completion or termination of the Study.

Should the Investigator rely on a third party for document archiving, he/she must notify the Sponsor of the storage location and the procedure for transferring the file.

11 Data Management

No later than the Study Initiation Visit, the Sponsor will provide, free of charge, an electronic data capture system (eCRF), named **Symphony**, in which all data pertaining to the present Clinical Investigation will be collected.

Symphony is an Electronic Data Capture (EDC) solution developed and validated by **Arithmos Srl**, a company certified according to ISO 9001 and ISO 27001 standards. Symphony therefore operates under an Information Security Management System compliant with international regulatory standards, and ensures regulatory adherence by monitoring and archiving the audit history directly within the platform.

For further details, please contact:

ARITHMOS Srl

[name]

[contact]

[contact]

E-mail: [contact]

No later than the Study Initiation Visit, the Sponsor will provide Investigators with the necessary training for the proper use of Symphony. If required, the Sponsor will also maintain a free help desk service throughout the duration of the Clinical Investigation to support Investigators.

Each Investigator will be able to access Symphony via the internet using personal login credentials and will only have visibility of the data relating to patients enrolled at their own site.

The clinical data collected within the present Clinical Investigation will be processed by the Sponsor in an anonymised form, in compliance with European data protection legislation, namely Regulation (EU) 2016/679 – the General Data Protection Regulation (GDPR).

12 Quality Assurance

In order to ensure the proper conduct of the Clinical Investigation in compliance with Good Clinical Practice, UNI EN ISO 14155:2019 and subsequent updates, and in accordance with the provisions of the present Clinical Investigation Plan, the Sponsor:

- has established a monitoring plan (as described above);
- furthermore, if deemed necessary, either during or after the active phase of the Investigation, the Sponsor's Quality Assurance Department (as well as national or international regulatory authorities) may conduct an audit at the Site, with at least 15 days' prior notice.

13 Protocol Deviations

All deviations from the present Clinical Investigation Plan, whether identified by the monitor during site visits or spontaneously reported by the Investigator, will be recorded by the Sponsor and retained within the study-related documentation.

Each deviation will be assessed by the Sponsor and classified as either a major or a minor deviation. Following this evaluation, the Sponsor will implement corrective actions as required by Good Clinical Practice (GCP) to prevent recurrence and, if necessary, will promptly inform all Investigators and the relevant Ethics Committee.

Furthermore, at the conclusion of the Clinical Investigation, the list of deviations will be reviewed to determine whether any of them may have compromised the interpretation of the affected results.

14 Amendments

In the event that amendments to the present Clinical Investigation Plan become necessary, the Sponsor shall:

- classify the nature of the amendments as substantial or non-substantial;
- revise the Clinical Investigation Plan and any study documentation impacted by the amendments, ensuring that all changes are appropriately tracked;
- in the case of non-substantial amendments, promptly notify in writing the participating Site and the corresponding Ethics Committee for information purposes, providing copies of the revised documents;
- in the case of substantial amendments, suspend the Clinical Investigation until a new favourable opinion has been issued by the relevant Ethics Committee.

15 Adverse events

The foreseeable adverse events related to the use of the 8-Plate Plus, as identified through the risk analysis performed during product design, are described in the section “POSSIBLE ADVERSE EFFECTS” of the device’s Instructions for Use (http://abs.orthofix.it/db/resources/PQ_EPP.pdf).

This Clinical Investigation is a retrospective observational study and, therefore, does not pose additional risks to patients or Investigators.

Definitions:

- An *adverse event (AE)* is any undesirable experience associated with the use of the device in a patient.
- An *adverse event* is defined as a *serious adverse event (SAE)* when, as a consequence of such event, the patient:
 - dies;
 - experiences a life-threatening event;
 - requires prolongation of hospitalisation;
 - requires re-hospitalisation;
 - suffers permanent disability;
 - experiences a congenital anomaly or birth defect.

Expected Serious Adverse Device Effects (SADEs) — i.e., those already reported in the device Instructions for Use — are further classified as **E(SADE)** (*Expected SADE*). Conversely, Serious Adverse Device Effects not previously reported in the device Instructions for Use are further classified as **U(SADE)** (*Unexpected SADE*).

All adverse events and adverse device effects associated with the use of the device that occurred during the entire observation period of the Clinical Investigation will be classified and reported to the Sponsor via the electronic database provided by the Sponsor.

Since this is a retrospective Clinical Investigation, serious adverse events (SAEs), having already followed the reporting procedures of the vigilance system, are not subject to prompt notification upon awareness, as otherwise required by GCP (Section 4.11.1).

16 Statistics

The safety profile of the 8-Plate Plus, as measured in the present Clinical Investigation, will be compared with the safety data reported in the scientific literature for the treatment of lower limb deformities by guided growth performed with equivalent tension-band plates.

The sample size calculation was performed in order to estimate the confidence intervals for the primary endpoint (safety outcome related to treatment response) of the 8-Plate Plus and to enable a reliable comparison with the data reported in the literature.

Accordingly, the sample size was determined by estimating the number of implants required so that the confidence intervals for the study primary endpoint with the 8-Plate Plus would fall within the established safety profile for this treatment, namely within the range of safety data reported in the literature for its predecessor (the GGS) and for equivalent medical devices.

Specifically, the scientific literature indicates that the proportion of patients treated with a tension-band plate for lower limb deformity who experience at least one device-related complication ranges between 3% and 12%, depending mainly on the heterogeneity of the underlying diagnosis.

Assuming that the expected proportion of patients experiencing at least one complication with the 8-Plate Plus is 3%, the sample size calculation showed that, in order for the upper limit of the 95% confidence interval for the primary endpoint (calculated using the exact binomial method) to remain below 12% (i.e., 9.94%), a total of 70 implants (in approximately 40 patients) are required.

The clinical data collected during the present Clinical Investigation will be analysed using descriptive statistics:

- the primary endpoint will be presented as a percentage value with its corresponding 95% confidence interval;
- the secondary endpoint will be presented as a percentage value with its corresponding 95% confidence interval.

The clinical data obtained from this Clinical Investigation will be used to complete the evaluation of the clinical performance and safety of the 8-Plate Plus, with the objective of confirming that the device can be considered safe and effective as hypothesised during its development, based on the preclinical evaluations conducted for CE marking.

17 Publication of Results

The Investigators and the Sponsor agree to maintain the clinical data collected during the present Clinical Investigation as confidential until such information is made publicly available, in anonymised form, by the Sponsor at the conclusion of the Investigation.

Within four months of the last site close-out visit, the Sponsor will be responsible for making the Investigation data public through the preparation of the final clinical report, containing aggregated and analysed site data, which will be provided to the Investigators, the involved Ethics Committee, and the Competent Authority.

Furthermore, within six months of the finalisation of the clinical report, the Sponsor reserves the right to publish a manuscript containing the aggregated and anonymised data from the monocentric study.

At the end of the Investigation, the Sponsor will make available to the Site the results pertaining to the patients enrolled in the study for publication purposes.

The Sponsor reserves the right to present the results of this study at scientific meetings and to submit these data to national and international authorities. At the same time, the Sponsor acknowledges the right and interest of all participating Investigators to publish scientifically, or to disseminate at congresses and meetings, the results obtained from the present Clinical Investigation.

18 Data Publication Policy

The Sponsor undertakes to share with all Investigators, for information and review, any preliminary version of the manuscript prior to publication.

Any publication by an Investigator may take place only after the potential publication by the Sponsor. It is understood that:

- the Investigator may initiate a publication prior to the Sponsor's publication only with the Sponsor's written consent;
- if, within six months from the finalisation of the clinical report, the Sponsor has not initiated any publication, the Investigator shall be free to publish the results obtained at his/her Site without requiring the Sponsor's written consent.

Prior to any publication or presentation of results, Investigators agree to submit in due time (in any case not less than 30 days before publication or presentation) the manuscript/abstract/presentation to the Sponsor for review and approval. The Sponsor undertakes to provide feedback within 15 days of receipt of the draft.

